	
RECIST 1.1 response, and an over 90% chance of at least 2 subjects having a response. All subjects who take at least one dose of study drug will be evaluable for safety and efficacy assessments.
 
Treatment-emergent AEs will be summarized using the Medical Dictionary for Regulatory Activities (MedDRA[®]) (Version 18.1 or higher) System Organ Class (SOC) and preferred term, classified from verbatim terms. The incidence and percentage of subjects with at least one occurrence of a preferred term will be included, according to the most severe grade using the National Cancer Institute Common Terminology Criteria for Adverse Events (NCI-CTCAE; Version 4.03). The number of events per preferred term will also be summarized. Causality (relationship to study treatment) will be summarized separately.
 
AEs, SAEs, related AEs, related SAEs, \geq Grade 3 AEs, related \geq Grade 3 AEs, and AEs leading to withdrawal, dose modification, or treatment discontinuation will be summarized by cohort and tesevatinib overall according to SOC and preferred terms. AEs will also be summarized in listings. Duration of AEs will be determined and included in listings, along with action taken and outcome.
 
Descriptive statistics including 95% confidence intervals for improvement in symptoms attributed to leptomeningeal metastases, clearing of NSCLC cells in the CSF, and clearing of CNS MRI findings will be presented. Exploratory evaluation of efficacy results by EGFR mutation will be performed.
 
In addition, identical statistics for the change and percent change from Cycle 1 Day 1 tumor measurements will be presented. These analyses will be done after each two cycles of therapy, and will include peripheral (non-CNS) tumors as well as brain metastases. Summary statistics will be produced for PFS and OS. The percentage of subjects without disease progression after 3 and 6 months of dosing will also be presented separately by local and central radiograph results.
 
Laboratory results will be classified according to NCI-CTCAE Version 4.03 and summarized by cohort. Laboratory results not corresponding to a coded term will not be graded. Incidence of laboratory abnormalities will be summarized. The worst on-study grade after the first dose of study drug will be summarized. The incidence of \geq Grade 3 laboratory abnormalities under treatment and shifts in toxicity grading from Cycle 1 Day 1 to highest grade post-Cycle 1 Day 1 will be displayed. Results for variables that are not coded will be presented in the listings as below, within, and above the normal limits of the local laboratory.
 
Vital sign measurements will be summarized at each scheduled time point using descriptive statistics. ECOG performance status results will be summarized by scheduled time point. Additional statistical details will be provided in a prospective statistical plan.
 
Tesevatinib concentrations in the plasma and CSF will be summarized at each scheduled collection time point using descriptive statistics, and displayed graphically.

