16.3.7 Safety Data

Safety analyses will be performed on all subjects who received any quantity of study drug. AEs that are not related to treatment and that occur more than 30 days after the administration of the last dose of treatment will not be reported or analyzed.

Safety analyses will present results by Cohort and, where appropriate, the three cohorts combined.

Safety observations and measurements include AEs, safety laboratory tests, vital sign measurements, physical examinations, pregnancy status, ECG assessments, and pharmacokinetic data.

Treatment-emergent AEs will be summarized using the Medical Dictionary for Regulatory Activities (MedDRA[®]) (Version 18.1 or higher) System Organ Class (SOC) and preferred term, classified from verbatim terms. The incidence and percentage of subjects with at least 1 occurrence of a preferred term will be included, according to the most severe grade using the National Cancer Institute Common Terminology Criteria for Adverse Events (NCI-CTCAE; Version 4.03). The number of events per preferred term will also be summarized. Causality (relationship to study treatment) will be summarized separately.

AEs, SAEs, related AEs, related SAEs, \geq Grade 3 AEs, related \geq Grade 3 AEs, and AEs leading to withdrawal, dose modification, or treatment discontinuation will be summarized by cohort and tesevatinib overall according to SOC and preferred terms. AEs will also be summarized in listings. Duration of AEs will be determined and included in listings, along with action taken and outcome.

Laboratory results will be classified according to NCI-CTCAE Version 4.03 and summarized by cohort. Laboratory results not corresponding to a coded term will not be graded. Incidence of laboratory abnormalities will be summarized. The worst on-study grade after the first dose of study drug will be summarized. The incidence of \geq Grade 3 laboratory abnormalities under treatment and shifts in toxicity grading from Cycle 1 Day 1 to highest grade post-Cycle 1 Day 1 will be displayed. Results for variables that are not coded will be presented in the listings as below, within, and above the normal limits of the local laboratory.

Vital sign measurements will be summarized at each scheduled time point using descriptive statistics. ECOG performance status results will be summarized by scheduled time point. Additional statistical details will be provided in a prospective statistical plan.

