## 2 Statistical Methods

No formal hypothesis testing will be conducted. Descriptive statistics including 95% confidence intervals for response rate, time-to-event and continuous measurements will be summarized by cohorts.

Tesevatinib concentrations in the plasma and CSF will be summarized at each scheduled collection time point using descriptive statistics, and displayed graphically.

AEs, SAEs, Grade 3&4 AEs, related AEs, related SAEs, related Grade 3&4 AEs, death, and AEs leading to withdrawal, dose modification, or treatment discontinuation will be summarized by cohort and overall according to high level terms (HLT) and preferred terms (PT). Adverse events will also be summarized in listings. Duration of AEs will be determined and included in listings, along with action taken and outcome.

Vital sign measurements will be summarized at each scheduled time point using descriptive statistics. The ECOG performance status results will be summarized by scheduled time point.

Laboratory results will be classified according to NCI-CTCAE Version 4.03 and summarized by cohort. The worst on-study grade after the first dose of study drug will be summarized. The incidence of ≥ Grade 3 laboratory abnormalities under treatment and shifts in toxicity grading from Cycle 1 Day 1 to highest grade post-Cycle 1 Day 1 will be displayed. Results for variables that are not coded will be presented in the listings as below, within, and above the normal limits of the local laboratory.

The table of list of tables, listings, and figures is displayed in Table 1.

 Table 1 Content of efficacy tables

| T/F/L | Number | Title   | Order                        | Population                    | Summary Statistics            |
|-------|--------|---|------------------------------|-------------------------------|-------------------------------|
| T     | 1.1.1  | Response rate by cohort   | Primary efficacy             | All treated subjects          | ORR, CR, PR, exact CI         |
| Т     | 1.1.2  | Response rate by visit and cohort                                   | Primary efficacy             | All treated subjects          | ORR, CR, PR, exact CI         |
| L     | 1.1.1  | Tumor size / symptoms and signs by visit and cohort                 | Primary efficacy             | All treated subjects          |                               |

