| L                                | Demo           | 2.1.1           | Demographics and baseline   | e characteristics              | All treated patients                      |  |
| L                                | Demo           | 2.2.1           | Medical history             |                                | All treated patients                      |  |
| L                                | Demo           | 2.3.1           | Disease history             |                                | All treated patients                      |  |
| L                                | CM             | 3.1.1           | Prior and concomitant med   | lications                      | All treated patients                      |  |
| Т                                | Exposure       | 4.1.1           | Treatment exposure and co   | ompliance by cohort            | All treated patients                      |  |
| L                                | Exposure       | 4.1.1           | Treatment exposure and co   | ompliance                      | All treated patients                      |  |
| L                                | Exposure       | 4.2.1           | Dose modifications          |                                | All treated patients                      |  |
| Т                                | AE             | 6.1.1           | Overall summary of TEAEs    | by cohort                      | All treated patients                      |  |
| Т                                | AE             | 6.1.2           | TEAEs by SOC/PT and coho    | rt                             | All treated patients                      |  |
| Т                                | AE             | 6.1.3           | Treatment related AEs by S  | OC/PT and cohort               | All treated patients                      |  |
| Т                                | AE             | 6.1.4           | Serious TEAEs by SOC/ PT a  | nd cohort                      | All treated patients                      |  |
| Т                                | AE             | 6.1.5           | Serious Treatment Related   | AEs by SOC/PT and cohort       | All treated patients                      |  |
| Т                                | AE             | 6.1.6           | Grade 3 and 4 TEAEs by SO   | C/PT and cohort                | All treated patients                      |  |

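### The SAP's severe-AE tables stop at Grade 4 where the protocol asks for Grade 3 and above, and the SAP names CTCAE Version 5 in two places against v4.03

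*SAP*

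**What the plan says.** **Grade cut.** Protocol Section 16.3.7 names the AE categories to be summarised: "AEs, SAEs, related AEs, related SAEs, \geq Grade 3 AEs, related \geq Grade 3 AEs" (the symbol is the extracted form of ≥). They are to be presented by cohort and overall: "will be summarized by cohort and tesevatinib overall according to SOC and preferred terms". The Synopsis, under Statistical methods, gives the same list. Neither place sets an upper grade.

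SAP Section 2 gives its own list: "AEs, SAEs, Grade 3&4 AEs, related AEs, related SAEs, related Grade 3&4 AEs, death, and AEs leading to withdrawal". SAP Table 2 follows that wording. The title of Table 6.1.6 begins "Grade 3 and 4 TEAEs by SO", and Tables 6.1.7, 6.1.10 and 6.1.11 have the same two-grade limit. For laboratory abnormalities, SAP Section 2 keeps the open-ended cut of Grade 3 or higher.

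**Scale version.** The protocol uses CTCAE v4.03 for toxicity grading (Synopsis, Safety assessments; Section 15.1), for AE and laboratory summaries (Section 16.3.7) and for the Cohort B symptom endpoint (Synopsis, Efficacy; Section 14.2). The SAP names Version 5 in 1.3.1.1, at the end of the sentence on when Cohort B symptoms are assessed, and again in 1.3.2 for grading toxicities. It uses v4.03 in the Cohort B primary objective (1.1.2), in the definitions of symptom improvement and progression (1.3.1.1) and for laboratory grading (Section 2).

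**The concern.** The incidence of AEs of Grade 3 or higher is a main tolerability figure in a single-arm phase 2 oncology study. The protocol defines it without a ceiling, and the SAP puts a ceiling at Grade 4. The protocol leaves further statistical detail to the SAP, but narrowing a named category changes it, and the SAP gives no reason. If fatal AEs carry Grade 5, the tables titled as severe AEs would show a lower incidence than the one the protocol specifies, and a reader of those tables alone could not tell.

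The version conflict is a smaller matter of the same kind. Read literally, AEs and laboratory results in one report would be graded on different versions, and the paragraph for the Cohort B primary endpoint names both.

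**Working it through.** The plan states no figure for severe-AE incidence, so there is nothing to reproduce. The check compares the texts, counts the affected outputs and sizes the possible effect.

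1. **Tables affected.** SAP Table 2 numbers its AE tables 6.1.1 to 6.1.11, so 11 tables. Four titles name a grade: 6.1.6 (all, by SOC/PT), 6.1.7 (related, by SOC/PT), 6.1.10 (all, by HLT) and 6.1.11 (related, by HLT). All 4 of 4 stop at Grade 4. The laboratory text in Section 2 and laboratory listing 7.1.1 both use Grade 3 or higher, so the cut is not uniform within the SAP.

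2. **Where a fatal AE would appear.** Protocol 15.3.1 treats death as the outcome of an AE, so the event remains an AE. Under the SAP it would enter the TEAE table (6.1.2), the serious TEAE table (6.1.4), the related tables (6.1.3, 6.1.5) if related, the AE listing (6.1.1), the death listing (6.1.4) and the separate death category in Section 2. If graded 5, it would not enter 6.1.6, 6.1.7, 6.1.10 or 6.1.11.

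3. **Size per subject.** Let k be the number of subjects whose only event of Grade 3 or higher is fatal, and n the number treated. The tabulated incidence falls short of the protocol's by k/n. The documents give no value for k, and k = 0 gives no shortfall. For k = 1:
   - full cohort, n = 20: 1/20 = 5.0 points;
   - all three cohorts full, n = 60: 1/60 = 1.7 points;
   - enrolment is up to 20 per cohort, so with an assumed n of 15 or 10: 1/15 = 6.7 or 1/10 = 10.0 points.

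   If fatal AEs were instead recorded as Grade 3 or 4 with a fatal outcome, the two definitions would coincide.

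4. **Can the two SAP categories be added?** With a subjects having a Grade 3–4 AE and d having a fatal AE among n, the incidence of Grade 3 or higher lies between max(a, d)/n and min(n, a + d)/n, because some subjects may have both. Taking a = 8, d = 3 and n = 20 purely as assumed values, the range is 8/20 = 40% to 11/20 = 55%, and the SAP's severe-AE table would show 40%. Adding the categories therefore does not give the protocol's figure. A subject-level count from the AE and death listings should.

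5. **Version count in the SAP.** Version 5 appears 2 times (1.3.1.1, 1.3.2). Version 4.03 appears 4 times (1.1.2 once, 1.3.1.1 twice, Section 2 once).

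**The case against.** The strongest reply is that the SAP divides severe AEs differently and loses nothing. Its list names death beside Grades 3 and 4, fatal AEs still reach the TEAE and serious TEAE tables and the listings, and with at most 60 subjects the combined count should be derivable by subject. No hypothesis test or decision rule uses this incidence. The step from fatal to Grade 5 is CTCAE convention that neither document states; the one grade table reproduced in the protocol, for QTc(F) in Section 5.2.1, ends at Grade 4. Protocol 15.3.1 also keeps disease progression out of SAE reporting, which may limit the number of fatal AEs. All of this stands, and it limits the consequence. It does not make the SAP's tables the ones the protocol asks for.

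Four stronger readings are tempting, and the documents do not support them.

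- *The SAP hides fatal events.* It does not, for the reasons just given.
- *Death is left undefined.* It sits in a list of AE categories to be summarised by high level and preferred term, so it most naturally means AEs with a fatal outcome. All-cause deaths have their own overall survival outputs (Table and Figure 1.2.2).
- *Promised AE summaries have been dropped.* The protocol asks for AEs by most severe grade ("The incidence and percentage of subjects with at least 1 occurrence of a preferred term will be included, according to the most severe grade") and for further categories ("and AEs leading to withdrawal, dose modification, or treatment discontinuation will be summarized by cohort and tesevatinib overall"), and Table 2 has no title specific to either. But SAP Section 2 itself commits to summarising AEs leading to withdrawal, dose modification or discontinuation, and table contents, including grade rows, are not described. This is missing detail in a list of outputs; it does not show that an analysis was omitted.
- *The Cohort B primary endpoint would be scored on a different scale.* The operative improvement and progression rules in SAP 1.3.1.1 both cite v4.03, sites grade on v4.03 under the protocol, and no regrading is described. Version 5 may be a labelling error.

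**Conclusion.** Two mismatches hold. First, the SAP's severe-AE category and all four grade-titled AE tables cover Grades 3 and 4, where the protocol specifies Grade 3 or higher. On the assumption that fatal AEs are graded 5, the tabulated incidence would differ from the protocol's whenever a subject's only event of Grade 3 or higher is fatal, at 5.0 points per such subject in a cohort of 20. The number of such subjects is unknown and may be zero. Second, the SAP names CTCAE Version 5 in two places, in conflict with the protocol and with itself. The documents do not show how the versions differ, so no effect on any grade can be claimed.

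Both should be corrected. Neither affects the efficacy definitions as written, and neither removes fatal events from the report.

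**What to change.** In SAP Section 2, replace Grade 3&4 with ≥ Grade 3 for both all and related AEs. Make the same change in the titles of Tables 6.1.6, 6.1.7, 6.1.10 and 6.1.11. Keep fatal AEs as a separate category as well, so that both the combined incidence and the fatal events can be read directly. In SAP 1.3.1.1 and 1.3.2, replace Version 5 with Version 4.03.

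The cost is a few words of SAP text and four table titles, with no new data collection. The one downside is that severe-AE rates may come out slightly less favourable. The change is best made before outputs are produced, so that the definition of severe-AE incidence is settled before the results are known.

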## Statistical Analysis Plan

| L | AE  | 6.1.2 | AE Leading to Treatment Discontinuation  | All treated patients |
|---|-----|-------|--|----------------------|
| L | AE  | 6.1.4 | Death  | All treated patients |
| Т | Lab | 7.1.1 | Lab values and their change from baseline by cohort Shifts in toxicity grading from baseline to highest grade post-baseline of | All treated patients |
| T | Lab | 7.1.3 | laboratory abnormalities by cohort   | All treated patients |
| L | Lab | 7.1.1 | Lab values with CTCAE grade >= 3   | All treated patients |
| T | VS  | 8.1.1 | Vital signs and their change from baseline by cohort   | All treated patients |
| L | VS  | 8.1.1 | Vital signs  | All treated patients |
| L | VS  | 8.2.1 | Physical examinations  | All treated patients |
| T | ECG | 9.1.1 | ECG parameters and their change from baseline by cohort  | All treated patients |
| T | ECG | 9.2.1 | QTcF abnormalities by cohort   | All treated patients |
| L | ECG | 9.1.1 | ECG values   | All treated patients |

Abbreviations: AE = adverse event; CNS = central nervous system; CSF = cerebrospinal fluid; CTCAE = Common Terminology Criteria for Adverse Events; DNA = deoxyribonucleic acid; ECG = electrocardiogram; EGFR = epidermal growth factor receptor; HLT = high level terms; MRI = magnetic resonance imaging; NSCLC = non-small cell lung cancer; OS = overall survival; PFS = progression-free survival; TEAEs = treatment-emergent adverse events; VS = vital signs
